6.8.1. Concomitant Pemphigus Therapy

All participants, regardless of treatment assignment, will concomitantly receive oral prednisone (or equivalent such as prednisolone) at 0.5 mg/kg qd as a starting dose. Except for oral prednisone (or equivalent), no other systemic therapies (eg, immunosuppressants, IVIg, immunoadsorption, anti-CD20 biologics) will be permitted during the trial.

At any post-baseline visit before DC is achieved, the prednisone dose will be adjusted by incrementing dosage according to clinical judgment, with the recommendation to increase by 1 or more steps (refer to [Table 3](#)) in case of disease progression or insufficient clinical change. To facilitate common judgments among investigators, recommendations for assessment of disease progression and insufficient clinical change are:

- Disease progression: increase of at least 5 in PDAI activity score compared to baseline score, observed at any post-baseline visit before DC.

- Insufficient clinical change: absence of DC after 3 to 4 weeks of the participant being treated at the starting baseline prednisone (or equivalent) dose or after 3 to 4 weeks of any new incremented dose of prednisone.

The recommendations of the prednisone dose escalation are:

- Stepwise escalation of daily prednisone dose by 1 or more steps according to clinical judgment in case of disease progression.
- Adjustment by incrementing dosage by 1 step according to clinical judgment in case of insufficient clinical change.
- Possible further escalation from the previous step by 1 or more steps, according to clinical judgment and under the same recommendation as above.
- Maximum escalation to 1.5 mg/kg qd for 3 weeks.

If, after a minimum of 3 weeks of oral prednisone at 1.5 mg/kg qd, DC is not attained, then the participant will be considered a treatment failure.

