The investigator should not implement any deviation from the concomitant oral prednisone (or equivalent) regimen, except for immediate safety concerns of the participants. After taking

appropriate action to ensure the safety of the participants, such concerns should be documented and communicated to the CRO's medical monitor and the sponsor.

Additionally, the following treatments may be used during the trial:

- Skin-directed topical corticosteroids
- Skin-directed topical antibiotics, antiseptics and moisturizers
- Buccal and mucosa-directed corticosteroids, antiseptics and anesthetics
- Analgesics
- Usual supportive treatments associated with intake of oral corticosteroids (eg, vitamin D, calcium, KCl, bisphosphonates) are intended to be used according to standard of care and current guidelines
- Non-live/non-attenuated vaccinations, and seasonal vaccinations (eg, influenza)

Table 3: Concomitant Prednisone Equivalent Doses (in mg) by Body Weight

Daily Prednisone Dose	Participant Body Weight (± 2.5 kg) ^a											Tapering Frequency	
	50 kg (47.5 – 52.4)	55 kg (52.5 – 57.4)	60 kg (57.5 – 62.4)	65 kg (62.5 – 67.4)	70 kg (67.5 – 72.4)	75 kg (72.5 – 77.4)	80 kg (77.5 – 82.4)	85 kg (82.5 – 87.4)	90 kg (87.5 – 92.4)	95 kg (92.5 – 97.4)	100 kg (97.5 – 102.5)		
1.5 mg/kg	75 mg	80 mg	90 mg	95 mg	105 mg	110 mg	120 mg	125 mg	135 mg	140 mg	150 mg	Tapering every 2 weeks	
1.25 mg/kg	60 mg	70 mg	75 mg	80 mg	85 mg	95 mg	100 mg	105 mg	110 mg	120 mg	125 mg		
1 mg/kg	50 mg	55 mg	60 mg	65 mg	70 mg	75 mg	80 mg	85 mg	90 mg	95 mg	100 mg		
0.75 mg/kg	35 mg	40 mg	45 mg	50 mg	50 mg	55 mg	60 mg	65 mg	65 mg	70 mg	75 mg		
0.5 mg/kg	25 mg	25 mg	30 mg	30 mg	35 mg	35 mg	40 mg	40 mg	45 mg	45 mg	50 mg		
0.3 mg/kg or 20 mg	20 mg	20 mg	20 mg	20 mg	20 mg	20 mg	25 mg	25 mg	25 mg	30 mg	30 mg		
0.2 mg/kg or 20 mg	Skip	Skip	Skip	Skip	Skip	Skip	20 mg	20 mg	20 mg	20 mg	20 mg		
Below 20 mg/day													
17.5 mg/day	17.5 mg	17.5 mg	17.5 mg	17.5 mg	17.5 mg	17.5 mg	17.5 mg	17.5 mg	17.5 mg	17.5 mg	17.5 mg		Tapering every week
15 mg/day	15 mg	15 mg	15 mg	15 mg	15 mg	15 mg	15 mg	15 mg	15 mg	15 mg	15 mg		
12.5 mg/day	12.5 mg	12.5 mg	12.5 mg	12.5 mg	12.5 mg	12.5 mg	12.5 mg	12.5 mg	12.5 mg	12.5 mg	12.5 mg		
10 mg/day	10 mg	10 mg	10 mg	10 mg	10 mg	10 mg	10 mg	10 mg	10 mg	10 mg	10 mg		

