1.2 STUDY DESIGN

This study is a prospective, multicenter, randomized, double-blinded, placebo-controlled study to investigate the efficacy, safety, participant outcome measures, tolerability, immunogenicity, PK, and PD of efgartigimod PH20 SC in adult participants with PV or PF.

The study comprises a screening period of up to 3 weeks, a treatment period of up to 30 weeks, and an 8-week follow-up period for participants who do not enrol into the open-label extension (OLE) study ARGX-113-1905.

After confirmation of eligibility, participants will be randomized in a 2:1 ratio to receive efgartigimod PH20 SC or placebo, as follows:

- Efgartigimod PH20 SC will be administered on day 1 and day 8 at a dose of [REDACTED] mg, followed by weekly administrations of 1000 mg until CRmin is observed. Efgartigimod PH20 SC will be administered at on-site visits until CR, with a minimum of 6 weekly on-site visits. After achieving CR, efgartigimod PH20 SC will be administered at on-site visits or at home by a nurse until CR on minimal therapy is achieved.
- Placebo (vehicle with 2000 U/mL of rHuPH20) SC will be administered using the same regimen.

CR is defined as the absence of new lesions and complete healing of established lesions (except for post-inflammatory hyperpigmentation or erythema from resolving lesions). CRmin is defined as the absence of new lesions and complete healing of established lesions while the participant is receiving minimal prednisone therapy of ≤ 10 mg/day for at least 2 months (8 weeks).

Randomization will be stratified by disease status (relapsing and newly diagnosed), disease severity (PDAI activity score < 30 and PDAI activity score ≥ 30), and body weight (< 77.5 kg and ≥ 77.5 kg) at baseline. Participants with severe PV or PF (PDAI activity score ≥ 45) will comprise a maximum of 30% of the overall study population.

All participants, regardless of treatment assignment, will concomitantly receive oral prednisone (or equivalent such as prednisolone) at 0.5 mg/kg qd starting dose. Except for oral prednisone (or equivalent), no other systemic therapies (eg, immunosuppressants, IVIg, immunoadsorption, anti-CD20 biologics) will be permitted during the study.

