2.2.2 Baseline and change from baseline

The baseline value will be the last available and non-missing value prior to the first dose of study medication. Assessments on day 1 without time collection or with time information exactly equal to the time of first IMP administration and which are planned predose will be considered as predose.

Change from baseline at time point t is defined as:

$$\text{value at time point } t - \text{baseline value}$$

Percentage change from baseline at time point t is defined as:

$$100 * ([\text{value at time point } t - \text{baseline value}] / \text{baseline value})$$

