3.2.2 Derivation rules

The following parameters will be derived:

- Time since pemphigus diagnosis (months): (date of first IMP – date of diagnosis)*12/365.25

Notes:

- Partially missing dates will be imputed as detailed in section 2.3.2.
- Result will be rounded as detailed in section 2.3.4 .
- Prior use of immunosuppressants is defined as use of medications with ATC level 2 = ‘IMMUNOSUPPRESSANTS’ and start date prior to first IMP administration
- Prior use of rituximab is defined as use of medication with CMDECOD = ‘RITUXIMAB’ and start date prior to first IMP administration
- Derivation of prednisone equivalent dose is detailed in section 3.5.2. Since day 1 can be considered as a transition day, prednisone equivalent dose on day 2 will be used as baseline.
- Region: North America (USA), Europe (Bulgaria, France, Hungary, Germany, Greece, Italy, Poland, Romania, Spain, UK), Asia (China, India, Japan), Rest of world (Australia, Georgia, Russian Federation, Serbia, Turkey, Ukraine)

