4.1.2.2 KEY SECONDARY ENDPOINTS (ALPHA CONTROLLED)

The following key secondary endpoints, which will be tested in the mITT population in hierarchical order (see section 4.1.4), are defined as:

- 1) The proportion of PV+PF participants that have achieved CRmin within 30 weeks using the same stratified CMH as for the primary endpoint. As this first key secondary endpoint is similar to the primary endpoint, the same approach for handling the main ICEs (both composite strategy and treatment policy strategy), as suggested for the primary analysis, will be applied.
- 2) Normalised cumulative Prednisone dose (NCPD, mg/kg/day) over the whole planned treatment phase in PV participants, will be analyzed by an analysis of covariance (ANCOVA) model to compare both treatment groups. Only actual administrations of prednisone are considered (not as scheduled). The model will include treatment and the stratification variables will be considered as factors.

Main intercurrent events are handled using the hypothetical strategy, that is, as follows:

- Intercurrent medications (see section 3.4.2): stop calculating cumulative dose after ICE. In case 'immunosuppressants for at least 4 weeks in total' is the ICE, use end of the 4 weeks IC medication as stop for cumulative dose calculation. In case ‘tetracyclines for at least 2 weeks in total' is the ICE, use end of the 2 weeks IC medication as stop for cumulative dose calculation. In case ‘IV or IM corticosteroids ' is the ICE, use the first day of this IC medication as stop for cumulative dose calculation.
- Discontinuation of IMP before CRmin due to lack of efficacy: stop calculating cumulative dose after this ICE.

Details on the derivation of intercurrent events are provided in Appendix 9.1.

	Statistical Analysis Plan	
ARGX-113-1904	Final analysis	Final 2.0 of 22NOV2023

A non-parametric stratified Mann-Whitney test will be performed as sensitivity analysis.

A supplementary analysis for this secondary endpoint will use the ‘treatment policy strategy’ where the occurrence of the intercurrent event is considered irrelevant: NCPD is calculated regardless of whether or not the intercurrent event occurs.

3) Time to CR in PV participants, calculated as the difference between the first date CR was achieved and the first IMP administration date.

Time to CR (days) = date (first CR) - first IMP date + 1

Main intercurrent events are handled as follows (composite strategy):

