Summary statistics on NCPD, cumulative prednisone dose, number of days and proportion of days with prednisone equivalent dose ≤ 10 mg will be provided for PV participants and an ANCOVA model with factors for treatment and the stratification variables will be applied on NCPD over the whole treatment phase only. Least square (LS) means and standard error (SE) with 95% 2-sided CI for placebo and efgartigimod will be reported, along with the difference in LS means of IMP vs placebo (with SE), 95% 2-sided CI, and 2-sided p-value. A non-parametric stratified Mann-Whitney test will be performed as sensitivity for PV participants. The 2-sided p-value resulting from this hypothesis test will signify whether the null hypothesis that the distributions of the NCPD for both treatment arms are identical can be rejected. The test will be conducted at a significance level of $\alpha=0.05$. A supplementary analysis using the treatment policy strategy applying the same ANOVA model will be done.

The table with summary statistics on NCPD will be repeated by subgroups, for PF participants and overall.

Time to CR and Time to DC will be descriptively presented with median times, quantiles and number and percentage of participants censored and with event. In addition, Kaplan-Meier survival plots by treatment arm will be produced (as in-text figures only). Both treatment groups will be compared using the stratified Fleming-Harrington weighted logrank statistic FH (1,0). Also the Cox proportional hazard model will be used: the model will include treatment as fixed effects and stratification factors as covariates. The HR for efgartigimod vs. placebo will be provided, along with the associated 95% 2-sided Wald-type CI and 2-sided p-value. The table will be produced for PV participants and overall. The descriptive statistics will also be presented by subgroups.

Duration of CRmin and other 'time to event' parameters of the 'other secondary endpoints' in section 4.1.2.3 will be descriptively presented and treatment groups will be compared using the logrank statistic.

	Statistical Analysis Plan	
ARGX-113-1904	Final analysis	Final 2.0 of 22NOV2023

Frequency tabulations will be provided for the percentages of treatment failure and its different reasons. Failure rates will be compared using the same CMH-test as for the primary endpoint analysis.

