9.2 SAS CODE

9.2.1 *MMRM model*

Calculate &meanbase. as mean of base of all unique participants in FAS.

[REDACTED]

9.2.2 *ANCOVA model*

[REDACTED]

Note: this is the script for NCPD. For other variables this code needs to be adapted according the model specifications in section 4.1. For example, for PDAI, the dependent variable is CHG and the baseline value needs to be added to the set of covariables.

9.2.3 *Time to event analysis: stratified Fleming-Harrington weighted logrank test*

[REDACTED]

9.2.4 *Time to event analysis: logrank test*

[REDACTED]

	Statistical Analysis Plan	
ARGX-113-1904	Final analysis	Final 2.0 of 22NOV2023

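### The alpha-controlled NCPD model uses baseline disease activity only as a cut at PDAI 30, and the SAP's baseline prednisone value is the day 2 protocol dose, so pre-trial prednisone dose is neither summarised by arm nor adjusted for

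*SAP*

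**What the plan says.** **The model.** SAP 4.1.2.2 item 2 defines the ANCOVA for NCPD in PV participants: "The model will include treatment and the stratification variables will be considered as factors". SAP 4.1.3 repeats it: "an ANCOVA model with factors for treatment and the stratification variables will be applied on NCPD over the whole treatment phase only". No continuous baseline term is named in either place. The code in SAP 9.2 is redacted, but its note says that "for PDAI, the dependent variable is CHG and the baseline value needs to be added to the set of covariables", which implies that the NCPD script contains no such term. The factors come from the design: "Randomization will be stratified by disease status (relapsing and newly diagnosed), disease severity" (SAP 1.2), with severity cut at PDAI activity 30, and body weight cut at 77.5 kg. In the fixed sequence of SAP 4.1.4, NCPD is position 3 in PV and position 6 in PV+PF.

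**The baseline dose.** The general rule in SAP 2.2.2 is: "The baseline value will be the last available and non-missing value prior to the first dose of study medication". For prednisone, SAP 3.2.2 departs from it: "Since day 1 can be considered as a transition day, prednisone equivalent dose on day 2 will be used as baseline". Protocol 6.8.1 says that all participants, in either arm, "will concomitantly receive oral prednisone (or equivalent such as prednisolone) at 0.5 mg/kg qd as a starting dose". Table 3 of the protocol ("Concomitant Prednisone Equivalent Doses (in mg) by Body Weight") converts this to milligrams by weight band.

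**Steroid history.** Inclusion criterion 4 (Protocol 5.1) admits four profiles: newly diagnosed and untreated, newly diagnosed on a first prednisone course, flaring off prednisone, and flaring on a tapered dose. SAP 3.4 tabulates and lists therapies started before the first dose, by ATC class and generic term (Table 14.1.2.5).

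**The concern.** NCPD is the first alpha-controlled continuous endpoint, and a miss at position 3 closes positions 4 to 8. Baseline disease activity plausibly predicts how much prednisone a participant will need, yet a continuous score is reduced to two groups.

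The baseline prednisone row looks as if it describes steroid history, but it is measured after randomisation and after the first IMP dose, on a regimen that the protocol has already standardised. The disease-status factor does not fill the gap. Its newly diagnosed level mixes untreated participants with those on a first course, and its flare level mixes those off prednisone with those on a taper. At stake are precision on NCPD and a reader's ability to see whether the arms differed in steroid dose at entry.

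**Working it through.** **1. The plan's own figure.** The documents give no SD, effect size or power for NCPD. The only power stated at this sample size is 95% for 183 PV participants (122 and 61), 34% versus 11%, two-sided 5% (Protocol 9.3). With pooled variance under the null:

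- Pooled proportion = (122 × 0.34 + 61 × 0.11)/183 = 0.263
- SE under the null = √(0.263 × 0.737 × (1/61 + 1/122)) = 0.0691
- SE under the alternative = √(0.11 × 0.89/61 + 0.34 × 0.66/122) = 0.0587
- Power = Φ((0.23 − 1.96 × 0.0691)/0.0587) = Φ(1.61) = 94.7%

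The figure reproduces. It concerns a responder analysis and does not carry over to NCPD.

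**2. How much the day 2 dose can vary.** The Table 3 starting doses are 25, 25, 30, 30, 35, 35, 40, 40, 45, 45 and 50 mg across bands from 47.5 to 102.5 kg. The extremes in mg/kg are:

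- Lowest: 25/57.4 = 0.436
- Highest: 25/47.5 = 0.526

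Within the table, the planned day 2 value per kg varies only by rounding.

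**3. Gain from continuous PDAI.** Let r be the correlation of log PDAI with NCPD, and c² the squared correlation of log PDAI with the indicator PDAI ≥ 30. Then:

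- Residual variance ratio, continuous versus cut = (1 − r²)/(1 − r²c²)
- Equivalent extra participants = 183 × r²(1 − c²)/(1 − r²)

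Both r and the PDAI distribution are assumptions. For log-normal PDAI truncated at 15 (for example median 28, log-SD 0.6, before truncation), c² is about 0.64. The last column starts from a comparison that has 80% power with the cut, and equals Φ(2.80/√ratio − 1.96).

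| r (assumed) | Variance ratio | Variance cut | Extra PV participants | Power, from 80% |
|---|---|---|---|---|
| 0.2 | 0.985 | 1.5% | 2.7 | 80.6% |
| 0.3 | 0.966 | 3.4% | 6.5 | 81.4% |
| 0.4 | 0.936 | 6.4% | 12.5 | 82.5% |
| 0.5 | 0.893 | 10.7% | 22.0 | 84.3% |

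Varying the median from 22 to 35 and the log-SD from 0.4 to 0.6 moves c² between about 0.58 and 0.67. The extra participants then run from about 2.5 (r = 0.2) to about 25 (r = 0.5).

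**4. Validity.** In 4,000 simulated trials of 122 versus 61 with no treatment effect, the rejection rate was 0.050 to 0.051, with or without a prognostic covariate (correlation 0, 0.3 or 0.5).

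**5. Chance imbalance.** The SE of a difference in any baseline variable is √(1/61 + 1/122) = 0.157 SD, so its 95% range is ±1.96 × 0.157 = ±0.31 SD. A difference of that size in pre-trial dose would not show in any planned summary table.

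**The case against.** The case for leaving the plan alone has real force.

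- **Prior steroids are reported.** One might infer that steroid history is not shown at all. It is: prior therapies appear by arm in a topline table and in a listing, and the exclusion of oral prednisone applies only to the concomitant table. Only dose is missing. This stands.
- **The PDAI and quality-of-life models are no precedent.** They analyse change from baseline, so a baseline of the same variable exists. NCPD accumulates from day 1 and has none. The protocol prespecified the same terms as an ANOVA (9.5.7), and the SAP uses the same model for flares and C-GTI. This stands: the plan is not inconsistent here. It leaves available precision unused.
- **Day 2 is a stated, reasoned exception.** It is descriptive and enters no efficacy model, so it cannot bias the test. It also shows whether the required starting dose was given. This stands, but it makes the value a starting dose and not a pre-treatment characteristic.
- **The gain is assumed.** This also stands. At the low end it is about three participants.
- **A single linear pre-trial dose term is hard to defend.** Zero covers both untreated participants and flaring participants off prednisone, while non-zero doses mix a failing first course with a taper. This stands, and it is why that term belongs in a sensitivity analysis and not in the alpha-controlled model.

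**Conclusion.** The point holds as one of precision and description. The NCPD model uses baseline activity only as a two-level factor. The baseline prednisone row reports a near-constant protocol dose. Pre-trial dose is neither summarised by arm nor adjusted for.

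A reader might go further and infer that the NCPD comparison is biased or its error rate inflated. The documents do not support that: allocation is randomised, the stratification factors are in the model, and the simulated type I error is about 5% either way.

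The benefit of continuous PDAI is a 1.5 to 11% cut in residual variance, or about 3 to 22 of 183 PV participants. This rests wholly on an assumed correlation of 0.2 to 0.5 and an assumed log-normal PDAI. No figure for the value of pre-trial dose can be taken from the documents. The change is worth making because it is nearly free, not because the analysis would otherwise fail.

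**What to change.** - **SAP 4.1.2.2 and 4.1.3:** add baseline PDAI activity score as a continuous covariate, for example on the log scale, to the NCPD ANCOVA in PV and in PV+PF. Specify this before unblinding.
- **Same sections:** add a sensitivity ANCOVA that also includes pre-trial steroid status (on/off, or the four inclusion profiles) and the last prednisone-equivalent mg/kg dose before day 1. Do not use the day 2 dose as a covariate: it is post-randomisation and nearly constant.
- **SAP 3.2.2 and 3.2.3:** summarise that pre-day-1 dose and the four profiles by arm, and relabel the day 2 value as starting dose.

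**Cost.** One degree of freedom in the main model and a little programming. Baseline PDAI is already collected. Medication dose is recorded from consent onward (Protocol 6.8 and 8), which should supply the last dose before day 1 for participants on prednisone during screening. For earlier therapy, Protocol 8.3.5 names start and end dates but not dose, so the proposal does not extend to lifetime exposure.
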